6.4 Benefit-Risk Considerations

Zamicastat is a newly developed reversible DBH inhibitor. Preclinical results suggest that PAH patients potentially benefit from zamicastat treatment.

Potential risks of study participation are experiencing an ADR to treatment with zamicastat. A detailed description of preclinical and clinical experience with zamicastat and of all treatment emergent adverse events (TEAEs) is provided in the IB. All reported related TEAEs were of mild or moderate intensity and resolved without sequelae. [4] No deaths and SAEs were reported. The safety of the patients will be monitored by a data safety monitoring board (DSMB).

In case of unusual symptoms or questions the patients can always contact the investigator and arrange an unscheduled visit (UV). The planned study procedures, standard examinations and questionnaires, will not pose a risk to the patients other than those associated with assessments in general common clinical practice.

This study will be performed in PAH specialised centres. The study will be conducted in compliance with this protocol, by study personnel who are qualified by education, training, and experience in their roles, with adherence to Good Clinical Practice (GCP), the applicable regulatory requirements, and ethical principles based on the Declaration of Helsinki.

7. STUDY OBJECTIVES

7.1 Primary Objective

The primary objective of this study is to evaluate the PK profile of different zamicastat doses in PAH patients to find the most promising therapeutic dosage range for the treatment of PAH disease.

7.2 Secondary Objectives

The secondary objectives of this study are:

1. To assess further PK parameters including apparent total clearance, terminal half-life and apparent volume of distribution
2. To assess the safety and tolerability of different zamicastat doses
3. To investigate the effect of different zamicastat doses on plasma D β H activity
4. To investigate the effect of different zamicastat doses on urinary catecholamine levels (norepinephrine and dopamine)
5. To investigate the change in pulmonary haemodynamic parameters
6. To investigate the change in the 6-minute walk test (6-MWT)
7. To investigate the change in biomarkers
8. To investigate the change in cardiac structure and contractibility, assessed by echocardiography
9. To investigate the change in quality of life, assessed by SF-36v2

8. STUDY DESIGN

8.1 Overall Study Design and Plan

This is an open-label, multi-centre study in patients with PAH who are currently on stable treatment with at least one PAH medication. It is planned to evaluate the PK profile (24-hour profile and trough levels) and the safety, tolerability and efficacy of four different zamicastat doses. Each patient will start treatment with the lowest dose (50 mg zamicastat once daily) and the dose will be up-titrated to the individual highest tolerated dose (HTD) i.e. up to 200 mg zamicastat once daily.

A DSMB will periodically review the safety data and will issue a recommendation if the doses can be used as planned.

This study will consist of:

- A screening period, 5 to 12 days: visit V1
- Up to four dose finding periods, 14 days each:
 - Dose A: visits A1, A2 and A3
 - Dose B: visits B2 and B3
 - Dose C: visits C2 and C3
 - Dose D: visits D2 and D3
- Maintenance period, 42 days: visits MPV1, MPV2 and MPV3
- Follow-up period:
 - Visit FU (down-titration): 14 days after MPV3 (only for patients taking 150 mg or 200 mg zamicastat who will not participate in the extension study)
 - Visit FU: 14 days after last IMP intake

After confirmed eligibility, patients will initiate treatment with Dose A (50 mg zamicastat once daily) at visit A1 and will be treated with this dose level for 14 days. If Dose A was considered safe by the investigator, it will be up-titrated to Dose B (100 mg zamicastat once daily) at visit A3 and the patient will continue with this dosage for 14 days. Patients not tolerating Dose A have to be withdrawn from the study.

The up-titration is based on safety criteria, including but not limited to:

- Absence of symptomatic and/or clinically relevant orthostatic hypotension
- Systolic blood pressure (SBP) > 95 mmHg or diastolic blood pressure (DBP) > 50 mmHg
- Absence of clinically significant changes in ECG parameters (heart rate, P-R interval, QRS duration, QT and QTc interval)
- Absence of clinically significant hypersensitivity/skin allergic reactions

After a positive safety evaluation at visit B3, the dose will be up-titrated to Dose C (150 mg zamicastat once daily) and the patient will continue on this dose level for a further 14 days. If Dose C was tolerated by the patient, it will be up-titrated at visit C3 to Dose D (200 mg zamicastat once daily) where the patient will remain for 56 days (14 days dose finding period + 42 days maintenance period).

Patients not tolerating their next dose at any time during the 14-days dose finding period will come immediately to the site or call the investigator (unscheduled visit), unless intolerance was detected during a scheduled visit and the dose will be down-titrated to the patient's previous

tolerated dose. Then they will continue this treatment for 42 days during the maintenance period.

The dose which will be taken during the maintenance period will be considered as an individual HTD.

At the end of the maintenance period, the patient will have the opportunity to continue treatment in an extension study (BIA-51058-202), which will be described in a separate protocol.

Patients not tolerating their individual HTD during the maintenance period have to be withdrawn from the study. An overview of the study design is provided in Figure 1.

8.2 Discussion of Study Design

Zamicastat is currently being developed for the treatment of cardiovascular disorders, including PAH. At this level, previous clinical experience with zamicastat includes phase I clinical studies in healthy volunteers in a wide doses range (5 mg to 2400 mg in single-dose conditions and 50 mg to 1200 mg in multiple-dose conditions), which were found to be well tolerated.

Nevertheless, patients with PAH frequently present an altered haemodynamic, as well as other individual factors, which may change the drug pharmacokinetics in relation to healthy volunteers.

Thus, in this study, PAH patients on stable treatment with at least one approved PAH therapy will be included and treated with the individual HTD zamicastat dose for 42 days during the maintenance period.

In a clinical study with healthy subjects, PK and PD analysis demonstrated that the dose range between 50 mg and 200 mg zamicastat once daily is the most promising therapeutic dose range, considering a D β H inhibition of 30-40% as the target pharmacodynamic effect. Moreover, it is expected that this dose range is considerably conservative to account for potential pharmacokinetic differences between PAH patients and healthy volunteers. Noteworthy, the maximum dose planned for PAH patients in the present clinical study (200 mg) is 6-fold lower than the maximum multiple-dose tested in healthy volunteers (1200 mg, study BIA-51058-105).

Bearing in mind the exploratory character of the study, the zamicastat dose will be increased in steps of 50 mg every 14 days up to the maximum dose of 200 mg zamicastat. Thereby, the dose increase is based on safety criteria to guaranty the safety of the patients. Additionally, the patient's safety will be supervised by a DSMB.

The treatment duration of 42 days at the individual HTD will be sufficient to investigate PK/PD parameters and safety aspects of zamicastat. Patients benefiting from treatment with zamicastat will be offered to participate in a subsequent extension study which will be described in a separate protocol.

8.3 Duration of the Study

First patient first visit (start date): May 2019

Last patient last visit (end of study): Nov 2020

9. STUDY POPULATION

9.1 Selection of Study Population and Diagnosis

This study will be performed in male and female PAH patients (WHO Group 1) aged 18 to 75 years, inclusive. The patients have to be on stable treatment with at least one approved PAH therapy within the 3 months before V1 (for details see Section 10.8.1). Additionally, patients have to be classified by the investigator as WHO functional class II or III according to ESC/ERS guidelines. [8] The sample size rationale is given in Section 13.3.

Patients will be enrolled in approximately 15 sites in 9 European countries. Other sites and other countries may be added as needed.

9.2 Inclusion Criteria

At **Visit 1 (Screening)**, patients must meet ALL of the following criteria:

1. Male or female patients aged 18 to 75 years, inclusive.
2. Able to comprehend and willing to sign an informed consent form (ICF).
3. Diagnosis of PAH (pulmonary arterial hypertension WHO Group 1) documented by RHC with a mPAP \geq 25 mmHg, a PAWP \leq 15 mmHg and a PVR $>$ 3 WU [8,9]:
 - a) Idiopathic, in non-vasoreactive patients
 - b) Heritable: Bone morphogenetic protein receptor type II (BMPR2) mutation and other mutations, in non-vasoreactive patients
 - c) Drugs and toxin induced, in non-vasoreactive patients
 - d) Associated with connective tissue disease
 - e) Associated with simple congenital defects (atrial septal defect and/or ventricular septal defect) if closed $>$ 12 months before inclusion.
4. The patient's last right heart catheterisation results, which were measured at the study site, must not be older than 90 days before V1 (will be considered as baseline value). Otherwise a right heart catheterisation has to be performed as part of the study at visit A1.
5. WHO functional class II or III as judged by the investigator.
6. Stable treatment with at least one of the following approved PAH therapies for at least 90 days prior to V1: Ambrisentan, Bosentan, Macitentan, Riociguat, Selexipag, Sildenafil, Tadalafil, Epoprostenol intravenous, Iloprost inhaled or Treprostinil intravenous or subcutaneous.
7. For women: Agree not to donate ova from the time of informed consent until 30 days after the last IMP intake.
For men: Agree not to donate sperm from the time of informed consent until 90 days after the last IMP intake.

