10.8 Prior and Concomitant Therapy

10.8.1 Previous therapy

Patients must be on stable treatment with at least one of the following approved PAH therapies for at least 90 days prior to V1:

- Ambrisentan
- Bosentan
- Epoprostenol intravenous
- Iloprost inhaled
- Macitentan
- Riociguat
- Selexipag
- Sildenafil
- Tadalafil
- Treprostinil intravenous or subcutaneous

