10.8.2 Concomitant medication

Treatment with the following medications and therapies is prohibited:

- CCBs, if taken for the treatment of PAH in vasoreactive patients.
- Drugs containing a catechol group that is metabolised by D β H e.g. rimiterole, isoprenaline, dopamine, dopexamine or dobutamide
- α - and/or β -blockers

The potential for drug interactions has not yet been assessed. Therefore, the use of concomitant medications should be cautiously evaluated and avoided whenever possible.

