## 2.4 Randomisation

No randomisation will be performed in this study.

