### 3 ANALYSIS SETS AND SUBGROUPS

#### 3.1 Analysis Sets

Within the framework of this study, the following analysis sets are defined and analysed:

**The Enrolled Set (ES)** will be defined as all patients who provided informed consent.

**The Safety Set (SS)** will be defined as all patients who belong to ES with at least one IMP administration.

**The Full Analysis Set (FAS)** will be defined as all patients who belong to SS with at least one efficacy assessment at visit MPV3.

**The modified Full Analysis Set (mFAS)** will be defined as all patients who belong to FAS with no substantial changes to their regimen of PAH-approved medications (including diuretics) between visits A1 and MPV3. These patients were defined during Data Review (see Data Review Report, Final 1.0, 10-MAR-2022).

**The Pharmacokinetic Analysis Set (PKS)** and **the Pharmacodynamic (PD) Analysis Set**, as well as all corresponding analyses, are described in the reporting and analysis plan prepared by Quotient Sciences Ltd.

Efficacy analyses will be performed on the FAS and mFAS, and the SS will be used for the analysis of the safety endpoints.

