### 5.3 Prior and Concomitant Medications

Prior and concomitant medications and therapies are documented in the eCRF.

The following information is collected:

- Medication / therapy
- Indication (Medical history condition, Adverse event, Other)
- Total daily dose
- Units
- Route

- Frequency
- Start date of medication
- Stop date of medication
- Ongoing (yes, no)

Medications and therapies will be classified as ‘prior’, ‘concomitant’ or ‘post-treatment’ based on start/stop dates:

- **Prior medications/therapies** are defined as those medications/therapies starting and ending prior to the first IMP intake.
- **Concomitant medications/therapies** are defined as medications/therapies started at or after first IMP intake and include medications/therapies started prior to the first IMP intake but continued during the study.
- **Post-treatment medications/therapies** are defined as medications/therapies which started after the last IMP intake.

If the start or stop date of a medication/therapy is incomplete or missing, it will be assumed to be concomitant except if the incomplete start or stop date indicates that the medication/therapy started and ended prior to the first IMP intake or started after the last IMP intake.

**PAH medications** will be defined as medications where the preferred term for the indication is “pulmonary arterial hypertension”, “congenital pulmonary hypertension”, or “pulmonary hypertension”, as well as any other medications taken for a condition related to PAH. These medications were selected manually during the Data Review (see Data Review Report, Final 1.0, 10-MAR-2022).

In addition, **PAH-approved** medications will be defined as those medications described in the protocol as being an approved PAH therapy (Ambrisentan, Bosentan, Macitentan, Riociguat, Selexipag, Sildenafil, Tadalafil, Epoprostenol intravenous, Iloprost inhaled or Treprostinil intravenous or subcutaneous) and diuretics. PAH-approved medications were selected manually during the Data Review (see Data Review Report, Final 1.0, 10-MAR-2022).

PAH-approved medications will be combined into groups of monotherapy, double therapy, triple therapy, etc., based on the number of PAH-approved medications taken at a given timepoint.

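### Criterion 6, read literally, asks for only one PAH drug to be stable; the effect of a second PAH drug started or changed before A1 cannot be separated from zamicastat in either FAS or mFAS

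*Protocol*

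**What the plan says.** Protocol 9.2, criterion 6, asks for "Stable treatment with at least one of the following approved PAH therapies for at least 90 days prior to V1" and then lists the drugs. Protocol 10.8.1 repeats it: "Patients must be on stable treatment with at least one of the following approved PAH therapies for at least 90 days prior to V1". Protocol 9.1 has a slightly different version: "The patients have to be on stable treatment with at least one approved PAH therapy within the 3 months before V1". The synopsis, Protocol 8.1 and deviation PD#06 in SAP section 6 also refer to at least one drug. No section says that every PAH drug the patient takes must be stable.

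The SAP looks at background therapy in two places. SAP 3.1 restricts the mFAS to FAS patients with "no substantial changes to their regimen of PAH-approved medications (including diuretics) between visits A1 and MPV3". SAP 5.3 groups patients into mono-, double and triple therapy "based on the number of PAH-approved medications taken at a given timepoint" and tabulates this at A1 and MPV3, so combination therapy is expected.

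There is no control group (SAP 2.4: "No randomisation will be performed in this study"). Efficacy is summarised as change from baseline with a 95% CI, on both FAS and mFAS (Protocol 13.4.2; SAP 3.1 and 5.5).

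**The concern.** Without a comparator, a change from baseline can be interpreted only if little else that affects the endpoint was changing. The 90-day stability rule is the main protection against drift from background therapy, and as worded it covers one drug.

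Take a patient established on one listed drug who began a second shortly before V1, or after the catheterisation that serves as baseline. That patient meets criterion 6 on its literal wording and raises no PD#06 deviation. If the second drug is still taking effect after baseline, and it helps, it moves PVR, walk distance, NT-proBNP and functional class in the direction a zamicastat benefit would. At stake is how the efficacy summaries are read. The primary pharmacokinetic objective does not rest on this comparison.

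**Working it through.** The plan gives no effect size, SD or power calculation, so there is no figure of its own to reproduce. The check is of coverage, then timing, then an illustration of size.

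**1. Does another provision close the gap?**
- Protocol 10.8.2 opens "Treatment with the following medications and therapies is prohibited" and names calcium channel blockers for PAH in vasoreactive patients, catechol drugs metabolised by DβH, and α- or β-blockers. Starting or changing a PAH drug is not listed. The remark that "the use of concomitant medications should be cautiously evaluated and avoided whenever possible" is advice, and its stated reason is drug interactions.
- Exclusion 12 (Protocol 9.3) covers an unstable medical condition in the investigator's opinion, not a recent change of drug.
- The mFAS window runs from A1 to MPV3. A drug started before A1 and held constant produces no change inside it.
- The therapy tables count drugs at A1 and MPV3. Such a patient appears as unchanged double therapy.

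**2. Where do the baselines lie relative to the mFAS window?**
- Walk test, NT-proBNP, echocardiography, functional class and SF-36v2 are assessed at V1, which is 5 to 12 days before A1.
- The baseline catheterisation is at A1 unless a study-site result from the 90 days before V1 exists (Protocol 9.2 criterion 4; 11.4.4).
- On the 200 mg path at nominal days, MPV3 falls 4 × 14 + 41 = 97 days after A1. That is 97 + 5 = 102 to 97 + 12 = 109 days after V1, and up to 90 + 12 + 97 = 199 days after the baseline catheterisation.
- The mFAS therefore leaves uncovered 5 to 12 days of the baseline-to-MPV3 interval for the V1 measures, and up to 90 + 12 = 102 days for haemodynamics. It also ignores changes just before baseline whose effect is still developing.

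**3. How large could the bias be? (assumed inputs)**
Let k patients of n = 32 be affected, and let d be the part of the second drug's effect that arises after baseline. The bias in the mean change is k·d/n. For PVR in dyn·s/cm⁵:
- k = 3, d = 100: 300/32 = 9.4
- k = 3, d = 200, or k = 6, d = 100: 600/32 = 18.8
- k = 6, d = 200: 1200/32 = 37.5

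The 95% CI half-width is t(0.975, 31)/√32 × SD = 0.361 SD: 54 for an assumed SD of 150 and 72 for 200. The ratio of bias to half-width runs from 9.4/72 = 13% to 37.5/54 = 69%.

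**4. What does that do to the interval?**
A simulation of 100,000 trials per setting used n = 32, no zamicastat effect and a second-drug effect of 0.5 to 1.0 SD. With 4 affected patients (bias 0.06 to 0.13 SD) the CI excluded zero in the favourable direction in about 5% to 8% of trials. With 8 (bias 0.13 to 0.25 SD) the figure was about 9% to 22%. The nominal rate is 2.5%. These inputs are also assumptions.

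**The case against.** - **The wording can be read the other way.** At least one may set the minimum number of drugs while stable describes the whole treatment, and some sites may have applied it so. This stands as a plausible reading. The text does not say it, so the point is a gap on the literal wording and not proof that such patients were enrolled.
- **The mFAS already deals with changing therapy.** This stands in part. A reader might infer that a second drug still being titrated during the study also escapes. The documents do not support that: titration continuing after A1 is a regimen change the mFAS can remove if it is judged substantial. It would then remain only in the FAS.
- **Nothing is credited to zamicastat.** A reader might infer that the plan attributes the second drug's effect to the study drug. It does not. Efficacy is secondary, exploratory and descriptive, with no test or decision rule, and an uncontrolled change supports no firm attribution however criterion 6 is worded. What stands is that the two effects cannot be separated.
- **The size is guesswork.** This stands. The documents give no number of recent add-ons, no effect size and no SD. Part of the second drug's effect may already be in the baseline, so only the remainder biases the change.

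**Conclusion.** The gap holds in a limited form. It concerns a second PAH drug started or changed before A1 and constant afterwards. Neither criterion 6 on its literal wording nor any other provision excludes that patient, and both FAS and mFAS keep the data. The exposure is greatest for haemodynamics when a catheterisation from before V1 serves as baseline.

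The bias is unknown. The 13% to 69% range follows entirely from the assumed 3 to 6 affected patients, 100 to 200 dyn·s/cm⁵ and SD of 150 to 200. It should not be collapsed to one typical value or read as an estimate for this trial. The analysed n may be below 32. For a fixed k the ratio varies as k/√n, so it rises if n falls.

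**What to change.** 1. **Protocol, for any further enrolment.** State in criterion 6 and in 10.8.1 that the stability requirement applies to all PAH-specific drugs taken at V1, and align the synopsis, 8.1 and 9.1. This cannot help patients already enrolled and does not by itself reach changes between V1 and A1.

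2. **SAP 3.1.** Add a labelled sensitivity analysis of the mFAS. It should also exclude patients with substantial changes in PAH-approved medications, including diuretics, at any time from 90 days before V1 through MPV3, or from the baseline catheterisation if that is earlier. Use the definition of substantial already applied for the mFAS. This covers V1 to A1. A catheterisation older than 90 days would deviate from criterion 4, but PD#04 classes that as minor and the criterion entered only with protocol version 3.0, so the clause is needed.

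Keep the mFAS itself unchanged. Its membership was settled at data review (report dated 10 March 2022) before the SAP was finalised on 22 March 2022, and in an open-label study a redefinition now would be a post-hoc exclusion. A labelled sensitivity analysis avoids that.

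**Cost.** No new data are needed: SAP 5.3 lists daily dose and start and stop dates among the collected fields. The analysis loses a few patients. If 6 of 32 were dropped, the half-width would go from 0.361 SD to t(0.975, 25)/√26 = 2.060/5.099 = 0.404 SD.

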9.3 Exclusion Criteria

Patients are to be excluded from the study for ANY ONE of the following reasons:

Criterion:

Rationale:

- | | |
|---|--|
| 
 1. Contraindication to zamicastat, i.e. known hypersensitivity to ingredients of zamicastat formulation. 2. Two or more consecutive measurements of SBP $<$ 95 mmHg or DBP $<$ 50 mmHg measured at V1. | 
Lack of suitability
 
Safety
 |
|---|--|

3. Uncontrolled diabetes mellitus with HbA1c \geq 8.5% within the last three months or at screening. Safety
4. PAH WHO Group 1 due to portal hypertension, human immunodeficiency virus (HIV) infection and schistosomiasis. Lack of suitability
5. Any disease known to cause pulmonary hypertension other than PAH WHO Group 1. Lack of suitability
6. Obstructive lung disease: Forced Expiratory Volume in 1 second/Forced Vital Capacity (FEV1/FVC) $<$ 60% and FEV1 $<$ 60% of predicted value after bronchodilator administration, as demonstrated and documented by previous spirometry data which, in the opinion of the investigator, represent the clinical state of the patient at the time of the screening visit. Safety
7. Restrictive lung disease: Total Lung Capacity (TLC) $<$ 70% of predicted value, as demonstrated and documented by previous spirometry data which, in the opinion of the investigator, represent the clinical state of the patient at the time of the screening visit. Safety
8. History of moderate to severe hepatic impairment (Child-Pugh B and C). Safety
9. Estimated glomerular filtration rate (eGFR) $<$ 30 mL/min/1.73 m² (measured at V1). Safety
10. Use of the following prohibited medication or treatments during study participation: calcium channel blockers (CCBs) if used for the treatment of PAH in vasoreactive patients; drugs containing a catechol group that is metabolised by D β H e.g. rimiterole, isoprenaline, dopamine, dopexamine or dobutamide or α - and/or β -blockers. Safety
11. Current or previous (within the past year) alcohol or substance abuse excluding caffeine or nicotine. Lack of suitability
12. Presence of any other significant or progressive/unstable medical condition that, in the opinion of the investigator, would compromise evaluation of the study treatment or may jeopardise the patient's safety, compliance or adherence to protocol requirements. Safety
13. For women: Pregnancy or breast-feeding. Women of childbearing potential (as defined in Section 4.2) unable or unwilling to undergo pregnancy tests and practice highly effective contraceptive measures in combination with a barrier method e.g. condom (without spermicidal foam/gel/film/cream/suppository or fat- or oil-containing lubricants), occlusive cap (diaphragm or cervical/vault caps) with spermicidal gel/film/cream/suppository from the time of informed consent until 30 days after last IMP intake. Highly effective methods for women are surgical intervention (e.g. bilateral tubal occlusion), non-hormonal implantable intrauterine device, true sexual abstinence (i.e. when this is in line with the preferred and usual lifestyle of the patient) and vasectomised partner (provided that the partner is the sole sexual partner of the patient and the partner has received medical assessment of the surgical success). Periodic abstinence (e.g.

calendar, ovulation, symptothermal, post-ovulation methods), hormonal contraceptives and withdrawal are not acceptable methods of contraception.

For men: Male patients who are sexually active with a partner of childbearing potential must use, with their partner, a condom plus an approved acceptable contraceptive measure from the time of informed consent until 90 days after the last IMP intake. The following methods are acceptable methods of contraception: partner's use of combined (oestrogen and progestogen-containing) hormonal contraception associated with inhibition of ovulation (oral, intravaginal, transdermal); partner's use of progestogen-only hormonal contraception (oral, injectable/implantable, intrauterine hormone-releasing system); partner's use of implantable intrauterine device; surgical sterilisation (for example, vasectomy or bilateral tubal occlusion).

- | | |
|---|---|
| 14. Previous participation in any other drug investigational study within the past 30 days (or five half-lives of investigational medicinal product [IMP] whichever is longer) prior to V1. | Lack of suitability |
| 15. Vulnerable patients according to Section 1.61 of the ICH guideline for Good Clinical Practice E6 | Vulnerable patients according to GCP 1.61 |

